12.3 Statistical Analysis

12.3.1 General Considerations

Continuous variables will be summarized using the following descriptive summary statistics: the number of subjects (n), mean, SD, median, minimum value (min), and maximum value (max). The precision of the measurement for each continuous variable will be specified in the SAP. Unless otherwise specified, min and max values will be reported with the same precision as the units of the raw data. The mean, median, and SD will be reported to 1 additional decimal

place. Any values that require a transformation to standard units (metric or SI) will be converted with the appropriate precision.

Categorical variables will be summarized using counts and percentages. Percentages will be presented to 1 decimal place.

The baseline value, unless otherwise specified, will be the most recent non-missing measurement (scheduled or unscheduled) collected before the first dose of study drug in the parent study. For assessments collected in replicates, the baseline will be defined as the average of non-missing values.

Change (absolute change) from baseline will be calculated as post-baseline value – baseline value.

The **Efficacy Analysis Period** for each Part will include the time from the first dose of study drug to the last scheduled efficacy visit in the corresponding Part, unless otherwise specified.

The **Treatment-emergent (TE) Period** for each Part will include the time from the first dose of study drug to 28 days after the last dose of the study drug or to the date of completion of study participation in the corresponding Part (as defined in Section 9.1.5), whichever occurs first.

Part A and Part B data will be analyzed separately, using the respective analysis set, efficacy analysis period, and TE period for each Part. For analysis of the number of PEx, events in the parent study and this study (Parts A and B, as applicable) may also be combined.

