12.3.3.2 Analysis of Secondary Efficacy and Pharmacodynamic Endpoints

The secondary endpoints will be analyzed separately for each Part.

- Absolute change in ppFEV₁**

One of the secondary efficacy endpoints is the absolute change from baseline in ppFEV₁ at visits in this open-label study, for subjects who receive at least 1 dose of study drug in each Part. The primary analysis for this secondary endpoint will be based on a mixed-effects model for repeated measures (MMRM), with the absolute change from baseline in ppFEV₁ as the dependent variable for visits in each Part. The model will be similar to the one used in the parent study.

The details including sensitivity analyses and supportive analysis will be described in the SAP.

- Absolute change in SwCl**

Analysis of this PD endpoint will be based on an MMRM similar to the one used in the parent study.

- Absolute change in CFQ-R RD score**

Analysis of this endpoint will be based on an MMRM similar to the one used in the parent study.

- Absolute change in BMI and BMI-for-age z-score**

Analysis of this endpoint will be based on an MMRM similar to the one used in the parent study.

- Number of PEx and CF-related hospitalizations**

Analysis of this endpoint will be based on summary statistics. Additional analysis may be provided and details will be discussed in the SAP.

- Absolute change in LCI_{2.5}**

Analysis of this endpoint will be based on an MMRM similar to the one used in the parent study.

- Absolute change in weight and weight-for-age z-score**

Analysis of this endpoint will be based on an MMRM similar to the one used in the parent study.

- Absolute change in height and height-for-age z-score**

Analysis of this endpoint will be based on an MMRM similar to the one used in the parent study.

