3 MODIFICATIONS

3.1 Modifications to the Approved Clinical Study Protocol

Section 12 of the Clinical Study Protocol (CSP, Version 2.0) states that data from Part A and Part B will be analyzed separately. In this SAP Version 3.0, safety data in Part A and Part B data will be pooled together to provide a comprehensive safety analysis for the entire Study 445-107.

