8.2.3 Full Analysis Set

The **Study 106 Full Analysis Set (106-FAS)** is defined the same as the FAS definition in the SAP of Study 106 Part B.

The **Open-label Extension Full Analysis Set (OLE-FAS)** is defined as all enrolled subjects who have received at least 1 dose of study drug in the OLE study.

The **(OLE) Cumulative TC Set** includes subjects who were enrolled and received at least one dose of study drug during the parent study (445-106 Part B) and/or received at least one dose of study drug during the OLE Study.

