9.2 Analysis Period for Part A Analysis

OLE Efficacy Period for Part A: Time from the first dose of study drug in the corresponding Part until the last efficacy assessment, which may be collected up to the corresponding Week 96 Visit or the earlier of Day 673 and the end of study participation if subject does not have the corresponding Week 96 Visit in the same Part. This analysis period will be used with the OLE-FAS for the corresponding Part to analyze efficacy data during the corresponding Part.

OLE Safety Period for Part A: Time from the first dose of study drug in the corresponding Part to 28 days after the last dose of the study drug in the corresponding Part or to the completion date of study participation (as defined in Section 9.1.5 of the CSP), whichever occurs first.

The completion date of study participation will be obtained from the end of study page of the eCRF.

The **Treatment-emergent (TE) Period for Part A** is same as the OLE Safety Period for the corresponding Part.

Cumulative TC Efficacy Period for Part A: For subjects who enrolled in Part A, the time from the first dose of study drug in the parent study (445-106 Part B) until the last efficacy assessment in Part A, which may be collected up to the Part A Week 96 Visit or the earlier of Day 673 in Part A and the end of study participation if subject does not have the Part A Week 96 Visit. For subjects who did not enroll in the OLE study and were enrolled and received study drug in the parent study, definition of this analysis period is the same as the parent study efficacy period.

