Height z-score and Weight z-score: the height z-score and weight z-score, adjusted for age and sex, will be referred to as weight-for-age z-score (weight z-score) and height-for-age z-score (height z-score). The weight z-score and height z-score will be calculated by using Centers for Disease Control and Prevention (CDC) growth charts⁷, with the age (in months) used for the calculation defined in Appendix A.

Pulmonary exacerbation (PEx): A PEx is defined as a new or changed antibiotic therapy (intravenous [IV], inhaled, or oral) for any 4 or more of the following signs/symptoms:

- Change in sputum
- New or increased hemoptysis
- Increased cough
- Increased dyspnea
- Malaise, fatigue, or lethargy
- Temperature above 38°C (equivalent to approximately 100.4°F)
- Anorexia or weight loss
- Sinus pain or tenderness
- Change in sinus discharge
- Change in physical examination (PE) of the chest
- Decrease in pulmonary function by 10%
- Radiographic changes indicative of pulmonary infection

The number of PEx is then defined as the total number of PEx during the Cumulative TC Efficacy period.

Lung clearance index (LCI): the LCI assessments are derived from N₂-multiple-breath washout (MBW) testing. Each MBW will be performed in multiple replicates for each visit and the final LCI value will be calculated from the technically acceptable washout replicates as graded and determined by a central reader. The following algorithm is used to derive the LCI values at each visit based on the multiple replicates:

- When there is only one acceptable replicate at the visit, the LCI values will not be calculated. The assessment for that subject at the corresponding visit will be missing.
- Where there are 2 or more acceptable replicates at the visit, the mean of the values for the acceptable replicates will be calculated as the LCI value at the corresponding visit.

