Analysis of these variables will be based on an MMRM similar to the analysis of the absolute change in ppFEV₁ from baseline with the corresponding baseline included as a covariate instead of baseline ppFEV₁. The analysis will be conducted with clinic assessed data only. An additional analysis may be

performed to include data obtained in clinic and at home using the scales and stadiometers provided by Vertex, if the home assessed data are reasonably consistent with the clinic assessed data.

Number of PEx and CF-related hospitalizations:

The analysis of PEx will be based on Cumulative TC Set for Part A, and for the Cumulative TC Efficacy Period for Part A.

PEx will be summarized as described below:

- Number of events:
 - Number of PEx
 - Number of PEx requiring hospitalizations
 - Number of PEx requiring IV antibiotic therapy
 - Number of PEx requiring hospitalization or IV antibiotic therapy
- Duration of events:
 - Number of days with PEx
 - Number of days with PEx requiring hospitalizations
 - Number of days with PEx requiring IV antibiotic therapy
 - Number of days with PEx requiring hospitalization or IV antibiotic therapy

CF-related hospitalizations will be summarized as described below:

- Number of events:
 - Number of planned hospitalizations for CF (i.e., antibiotic therapy)
 - Number of unplanned hospitalizations for reasons other than antibiotic therapy for sinopulmonary signs/symptoms
- Duration of events:
 - Number of days of planned hospitalizations for CF (i.e., antibiotic therapy)
 - Number of days of unplanned hospitalizations for reasons other than antibiotic therapy for sinopulmonary signs/symptoms

For number of events variables, subjects with multiple defined events during the PEx analysis period will be counted multiple times. The annualized duration of events for each subject will be the total number of days with the defined events times 48 weeks divided by the total number of weeks on study up to the end of the PEx analysis period.

Absolute change in LCI_{2.5} from baseline:

Analysis of this variable will be based on an MMRM similar to the analysis of the absolute change in ppFEV₁ from baseline with the baseline LCI_{2.5} included as a covariate instead of baseline ppFEV₁.

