Absolute change in height and height-for-age z-score from baseline:

Analysis of these variables will be based on an MMRM similar to the analysis of the absolute change in ppFEV₁ from baseline with the corresponding baseline included as a covariate instead of baseline ppFEV₁. The analysis will be conducted with clinic assessed data only. An additional analysis may be performed to include data obtained in clinic and at home using the scales and stadiometers provided by Vertex, if the home assessed data are reasonably consistent with the clinic assessed data.

Number of PEx and CF-related hospitalizations:

The analysis of PEx will be based on OLE Cumulative TC Set and for the OLE Cumulative TC Efficacy Period.

PEx will be summarized as described below:

- Number of events:

- Number of PEx
- Number of PEx requiring hospitalizations
- Number of PEx requiring IV antibiotic therapy
- Number of PEx requiring hospitalization or IV antibiotic therapy
- Duration of events:
 - Number of days with PEx
 - Number of days with PEx requiring hospitalizations
 - Number of days with PEx requiring IV antibiotic therapy
 - Number of days with PEx requiring hospitalization or IV antibiotic therapy

CF-related hospitalizations will be summarized as described below:

- Number of events:
 - Number of planned hospitalizations for CF (i.e., antibiotic therapy)
 - Number of unplanned hospitalizations for reasons other than antibiotic therapy for sinopulmonary signs/symptoms
- Duration of events:
 - Number of days of planned hospitalizations for CF (i.e., antibiotic therapy)
 - Number of days of unplanned hospitalizations for reasons other than antibiotic therapy for sinopulmonary signs/symptoms

For number of events variables, subjects with multiple defined events during the PEx analysis period (i.e., OLE Cumulative TC Efficacy Period) will be counted multiple times. The annualized duration of events for each subject will be the total number of days with the defined events times 48 weeks divided by the total number of weeks on study up to the end of the PEx analysis period.

Absolute change in LCI_{2.5} from baseline:

Analysis of this variable will be based on an MMRM similar to the analysis of the absolute change in ppFEV₁ from baseline with the baseline LCI_{2.5} included as a covariate instead of baseline ppFEV₁.

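### Pulmonary exacerbations are counted only cumulatively from the parent study, with no per-Part summary and no event rate, although the protocol has secondary endpoints analyzed separately for each Part

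*SAP*

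**What the plan says.** **Protocol.** Section 12.3.3.2 opens with the rule "The secondary endpoints will be analyzed separately for each Part" and lists the number of PEx and CF-related hospitalizations among those endpoints. The method for this endpoint is summary statistics, with further analysis left to the SAP. Section 12.3.1 says that Part A and Part B data are analyzed separately, each with its own set and period. For the number of PEx it adds that "events in the parent study and this study (Parts A and B, as applicable) may also be combined".

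**SAP.** Section 10.3.1.2.1 builds the cumulative period into the variable: "The number of PEx is then defined as the total number of PEx during the Cumulative TC Efficacy period". The Part A analysis follows suit in 10.3.1.2.2: "The analysis of PEx will be based on Cumulative TC Set for Part A, and for the Cumulative TC Efficacy Period for Part A". The final analysis, in 10.3.2.2.2, uses the corresponding cumulative set and period for the whole extension: "The analysis of PEx will be based on OLE Cumulative TC Set and for the OLE Cumulative TC Efficacy Period". The counting rule there covers every event-count variable, so CF-related hospitalizations are also totals over the cumulative period. Days with events are handled differently: each subject's days are multiplied by 48 weeks and divided by weeks on study.

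The cumulative set in SAP 8.2.3 takes in anyone dosed "during the parent study (445-106 Part B) and/or received at least one dose of study drug during the OLE Study". The only departure declared in SAP 3.1 is that "safety data in Part A and Part B data will be pooled together to provide a comprehensive safety analysis".

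**The concern.** The protocol makes the per-Part summary the rule and the combined summary an optional extra. For PEx, the SAP keeps the extra and drops the rule without saying so. The continuous secondary endpoints are treated as the protocol intends: SAP 10.3.2 gives them separate models for Part A and Part B.

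The study rationale (Protocol 5.2) includes durability. For PEx, durability means asking whether the event rate in the second 96 weeks resembles that in the first. A single total that accrues from the first parent-study dose grows with follow-up and cannot answer this. It also depends on how many subjects continued into Part B, which a count without a denominator does not reveal.

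**Working it through.** **1. What each analysis covers**

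| Source | PEx period | Denominator for counts |
|---|---|---|
| Protocol 12.3.1, 12.3.3.2 | each Part separately; combined as an option | none stated (summary statistics) |
| SAP 10.3.1.2.2 | parent + Part A | none |
| SAP 10.3.2.2.2 | parent + Part A + Part B | none |

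No PEx summary is specified for Part A alone or Part B alone.

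**2. Length of follow-up.** For subjects with a Part A Week 96 Visit, SAP 9.2 ends the Part A period there; for the others an upper day applies: "up to the Part A Week 96 Visit or the earlier of Day 673 in Part A". SAP 9.3 does the same with Day 1345. These days reproduce the design: (673 − 1)/7 = 96 weeks and (1345 − 1)/7 = 192 weeks. They are nominal lengths, since a Week 96 Visit may fall a few days later.

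The parent-study length is not in the documents. Assuming 12, 24 or 48 weeks, the ratio of full to parent-only follow-up is:
- 12 weeks: (12 + 192)/12 = 17
- 24 weeks: (24 + 192)/24 = 9
- 48 weeks: (48 + 192)/48 = 5

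**3. What the total hides.** Inputs are 64 enrolled subjects (SAP 7.2), 96 weeks per Part, and 365.25/7 = 52.179 weeks per year. Assume that all 64 complete both Parts. Patient-years per Part = 64 × 96/52.179 = 117.7. The rates below are invented for illustration.

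| Rate per patient-year, A / B | Events in A | Events in B | Total |
|---|---|---|---|
| 0.30 / 0.10 | 35.3 | 11.8 | 47.1 |
| 0.20 / 0.20 | 23.5 | 23.5 | 47.1 |
| 0.10 / 0.30 | 11.8 | 35.3 | 47.1 |

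A threefold fall, no change and a threefold rise give the same total.

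**4. Effect of retention.** Take 60 events and an assumed 24-week parent study.
- All 64 followed throughout: 64 × 216/52.179 = 264.9 patient-years, so 60/264.9 = 0.226 per patient-year.
- Only 40 contribute Part B time, in full: (64 × 120 + 40 × 96)/52.179 = 220.8 patient-years, so 60/220.8 = 0.272.

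The same count stands for different rates.

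**5. Precision of a per-Part rate.** With 24 events in 117.7 patient-years, the rate is 0.20 per patient-year, with an exact Poisson 95% CI of 0.13 to 0.30.

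**6. Annualized days.** 48/52.179 = 0.920, which is 8.0% below a calendar-year value. For example, 10 days over 216 weeks gives 10 × 48/216 = 2.22 as written and 10 × 52.179/216 = 2.42 per calendar year.

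**The case against.** The case for leaving the plan as it is has substance.

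- **Combining is allowed.** This stands. A reader might infer that the cumulative summary itself breaches the protocol; Protocol 12.3.1 expressly permits it. The fault is the missing separate summary.
- **The endpoint is a number, and the protocol asks only for summary statistics.** This also stands. A reader might infer that the protocol requires a rate; it does not. Even for adverse events it makes exposure-adjusted rates optional (12.3.4.1), and it was the SAP that chose to include them. The rate is a recommended addition, whereas the per-Part summary is a protocol commitment.
- **Follow-up is already adjusted for.** This is partly true. A reader might infer that PEx is reported only as a raw total, but the counts are split by hospitalization and IV antibiotic use, and days with events are scaled to weeks on study. Those days measure duration rather than number, and they too are pooled across the whole period.
- **Period figures can be recovered.** They can, approximately. SAP 9.1 defines a parent-study efficacy period. The final count minus the Part A count approximates Part B events, and the patient-years in SAP 10.2.2.5 minus those in 10.2.1.5 approximate Part B exposure. This subtraction is not planned, spans separate analyses, and uses dosing time rather than PEx follow-up time.
- **The 48-week scaling is stated openly and may be a parent-study convention.** The parent SAP is not available, so this cannot be excluded. Comparisons of days within the study are unaffected.

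A reader might also infer that SAP 11.1.2 leaves the PEx cutoff at the Week 144 interim unclear. It does not: the limit at Part B Week 48 is set by analysis visit, while a later sentence names PEx specifically and includes all available data, within the data cutoff.

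**Conclusion.** The point holds as a recommended correction to a descriptive secondary analysis. The SAP omits the per-Part summary of PEx and CF-related hospitalizations that Protocol 12.3.3.2 calls for, and SAP 3.1 does not list the omission. Without per-Part counts and person-time, the planned total cannot separate falling, stable and rising event rates.

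The 47.1-event illustration rests on full completion by 64 subjects and on invented rates. It shows that the total does not identify the trend; it does not predict a result. The follow-up ratios of 5 to 17 rest on an assumed parent study of 12 to 48 weeks. The omission of the per-Part summary rests on the text alone and needs none of these assumptions.

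The documents do not support a claim that the PEx data are lost or that any planned estimate is biased. The primary safety objective is untouched. The 48-week scaling is a labelling matter of 8.0%.

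**What to change.** 1. Keep the cumulative summary.
2. In SAP 10.3.2.2.2, add the number of PEx and of CF-related hospitalizations, with events per patient-year (365.25-day year), separately for Part A and Part B. In 10.3.1.2.2, do the same for Part A alone. Show the parent study alongside, using the period in SAP 9.1. Protocol 12.3.3.2 leaves room for the rate.
3. Assign each event to a period by its start date, and divide by the follow-up time of that same period. SAP 9.3 has no Part B-only efficacy period, so one must be written; Protocol 12.3.1 already defines an efficacy period for each Part. State where days between the Part A Week 96 Visit and a later Part B Day 1 belong.
4. If a cumulative-only summary is intended, list it in SAP 3.1 as a departure from the protocol, with the reason.
5. Label the annualized duration *per 48 weeks*, which changes no number, or scale it to 52.18 weeks.

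The cost is a few descriptive rows from data already collected, plus SAP wording. The downside is that events per period may be few, so rates will be imprecise; an exact Poisson confidence interval beside each rate would make that visible.

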10.3.2.2.3 Sensitivity Analysis

Not applicable because the primary endpoints are safety and tolerability assessments.

10.3.2.2.4 Analysis of Exploratory Efficacy Variables

Absolute change in FE-1 levels from baseline:

Summaries of observed values and change from baseline will be provided by visit. In addition, the number and percentage of subjects with shift changes from baseline (<15 mg/kg, \geq 15 mg/kg to <200 mg/kg, and \geq 200 mg/kg) at each post-baseline visit (<15 mg/kg, \geq 15 mg/kg to <200 mg/kg, and \geq 200 mg/kg) will also be provided.

Absolute change in serum levels of IRT from baseline:

Summaries of observed values and change from baseline will be provided by visit. In addition, the number and percentage of subjects with shift changes from baseline (<14ug/L, \geq 14ug/L to <40ug/L, and \geq 40ug/L) at each post-baseline visit (<14ug/L, \geq 14ug/L to <40ug/L, and \geq 40ug/L) will also be provided.

10.3.2.2.5 Analysis of Additional Efficacy Variables

Analysis of Additional Spirometry Variables

Summary statistics for raw values and for changes from baseline of the following spirometry measurements will be presented at each visit:

- FEV₁:
 - Absolute change from baseline in FEV₁ (L)
 - Relative change from baseline in FEV₁ (%)
 - Absolute change from baseline in percent predicted FEV₁ (percentage points)
 - Relative change from baseline in percent predicted FEV₁ (%)
- FVC:
 - Absolute change from baseline in FVC (L)
 - Relative change from baseline in FVC (%)
 - Absolute change from baseline in percent predicted FVC (percentage points)
 - Relative change from baseline in percent predicted FVC (%)
- FEF_{25-75%}:
 - Absolute change from baseline in FEF_{25-75%} (L/sec)
 - Relative change from baseline in FEF_{25-75%} (%)
 - Absolute change from baseline in percent predicted FEF_{25-75%} (percentage points)
 - Relative change from baseline in percent predicted FEF_{25-75%} (%)
- FEV₁/FVC:
 - Absolute change from baseline in FEV₁/FVC
 - Relative change from baseline in FEV₁/FVC (%)
 - Absolute change from baseline in percent predicted FEV₁/FVC (percentage points)
 - Relative change from baseline in percent predicted FEV₁/FVC (%)

Analysis of Other CFQ-R Variables

Summary statistics for raw values and for changes from baseline of the following CFQ-R domain scores will be presented at each visit.

- CFQ-R respiratory domain score (parent's version)
- CFQ-R non-respiratory domain score (child's version)
- CFQ-R non-respiratory domain score (parent's version)

Analysis of Additional LCI Parameters

Summary statistics for raw values and for changes from baseline of the following LCI parameters will be presented at each visit: LCI_{2.5}, LCI_{5.0}, and FRC.

